### 2.3 Background to the project:

Briefly discuss any previous research of relevance and cite no more than 4 key references.

Long COVID Syndrome (LCS) is a term now frequently utilized to describe the collection of chronic symptoms lingering at  $\geq 3$  months post-acute SARS-CoV-2 infection. Several studies detail the presence of multi-systemic chronic symptoms such as fatigue, reduced cognition, exercise intolerance, pain and tachycardia in this cohort. While much remains unknown regarding LCS, involvement of the autonomic nervous system has been suggested.

The Office for National Statistics, UK have found that as many as 1 in 10 individuals are likely to suffer these symptoms post SARS-CoV-2 infection consistent with LCS. With more than 108 million global cases of SARS-CoV-2 infection (as of February 13th 2021, Johns Hopkins Coronavirus Resource Center), there are potentially a high burden of LCS cases. Consequently, detailed characterization of this cohort of LCS patients is important as a high proportion of these individuals remain symptomatic with significant disability and unable to return to work.

Postural orthostatic tachycardia syndrome (POTS) is a heterogenous disorder characterized by chronic and disabling symptomatology that predominately affects young women of child bearing age. POTS onset has a reported association with antecedent viral illness as well as concomitant autoimmune disease. Onset of this multisystemic disorder has been described in a recent case report after SARS-CoV-2 infection. The pathophysiology remains unknown but may include post-viral autoimmunity, increased central sympathetic outflows, deconditioning/hypovolemia or neuro-endocrine related. Indeed, inflammatory biomarkers and

adrenergic and cholinergic antibodies have been reported in POTS and are of interest in the pathogenesis of post viral onset of this syndrome and the interplay with inflammatory pathways and neuroendocrine dysfunction.

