**Subject preparation:**

48 hr before examination the following will be discontinued

- Anticholinergics
- Sympathomimetics ( $\alpha$  and  $\beta$  agonists)
- Mineralcorticoids (Fludrocortisone)

24hr before examination the following will be discontinued

- Alcohol
- Salt tablets
- Caffeine
- Beta Blockers (propranolol, metoprolol), Ivabradine, Calcium channel blockers

[figure not shown]
8 hrs before testing

- Fast from food
- Drink only water 'to thirst' and abstain from fluid 'loading'

On the morning of testing

- No wearing of compression wear
- No abdominal binders
- No support stockings

Figure 1: Project Schema

As participants in this study are excluded from having other significant cardiac impairments or significant medical conditions, it is unlikely that drug cessation will cause any detriment other than the discomfort and inconvenience of poorly controlled orthostatic intolerance. Participants will be encouraged to discuss cessation of medications with their regular doctor. In addition, senior clinician researchers will identify those in the screening process who may have increased risk if medications are ceased. If it is decided that individuals are unable to cease the above listed medications for the prescribed time, then those participants will not be able to participate in the study. This is the case because biomarker and autonomic testing outcomes would not be deemed meaningful in the setting of artificial control of heart rate and fluid status.

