### **Inclusion Criteria**

Cohort 1 (LCS): Adults aged  $\geq 18$  years old (male or female); Able to provide written informed consent; previous SARS-CoV-2 infection (As some Australians contracted SARS-CoV-2 in countries that did not undertake testing in the early stages of the pandemic, some participants will not have a diagnosis by PCR. Inclusion with physician confirmed Long Covid is consistent with worldwide research practices for Long Covid studies); continuing chronic symptoms persisting for  $\geq 3$  months post-acute COVID-19 infection and not attributable to an alternative disease state.

Cohort 2 (POTS): Adults aged  $\geq 18$  years old (male or female); POTS diagnosis; Able to provide written informed consent; Diagnostic criteria for POTS met as per the following: 1. sustained heart rate elevation of  $\geq 30$  beats/min within 10 minutes. 2. No other secondary cause of these symptoms. 3. Absence of orthostatic hypotension 4. Symptomatology present for greater than 3 months

Cohort 3 (Healthy Control): Otherwise, healthy adults aged  $\geq 18$  years old (male or female); Able to provide written informed consent; absence of POTS diagnosis or previous SARS-CoV-2 infection.

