**Before study testing day:**

In addition, all study participants will be sent a link to a health questionnaire and QoL surveys as listed below. These can be done at leisure and without time restriction to reduce the effects of inconvenience and survey fatigue.

1. Holter Monitor: All patients will undergo 24 hour ambulatory ECG, at home (adhesive electrodes placed on the skin and attached to a recording device). This measure will be used to determine heart rate variability; which is a measure of baseline autonomic tone. It will also help to exclude other alternative cardiac arrhythmias.
2. Echocardiogram requires the subject to undertake an ultrasound of the heart previous to the day of testing at the subject's convenience. This test is important for determining other secondary causes of symptoms due to structural cardiac changes. It requires a non-invasive ultra-sound of the heart and generally takes 15 minutes to complete. To determine associations of neuroendocrine function with changes to orthostatic filling volumes and cardiac measurements. Echocardiogram will be undertaken in the semi-fowler position and then in passive leg raise (45 degree) position after 90 seconds.
3. Demographic survey and Medical Health History including alcohol consumption, tobacco use. Past medical history, medications and allergies will be completed by the two symptomatic cohorts.

Controls will complete a health history and demographic survey to confirm absence of exclusion medical conditions and medications when attending for assessment.

4. Rand SF-36: 36 item short form survey which is commonly utilised to measure self-reported quality of life measures in adult patients.
5. EQ-5D/5L: Is a short survey utilised and validated to describe and value health across 5 domains.
6. COMPASS-31: 31 question composite autonomic scale which is utilised widely for use in autonomic research and practice. It addresses the domains of: orthostatic intolerance, vasomotor, secretomotor, gastrointestinal, bladder and pupillomotor function.
7. Fatigue Severity Score: A 9 item questionnaire that reports how fatigue interferes with certain activities and rates the severity of fatigue.
8. 5 Point hypermobility screen: Five questions related to hypermobility. A score  $>2/5$  suggests hypermobility (sens 85%, spec 90%)

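### Minor: the visible preparation list controls caffeine and alcohol but not non-prescribed nicotine or strenuous exercise, and exposure on the test day is not recorded

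*Protocol*

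**What the plan says.** The preparation rules are in Protocol section 2.5, under Subject preparation, in four tiers.

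- "48 hr before examination the following will be discontinued": anticholinergics, sympathomimetics and mineralocorticoids.
- "24hr before examination the following will be discontinued": alcohol, salt tablets, caffeine, beta blockers, ivabradine and calcium channel blockers.
- Eight hours before: a food fast, and "Drink only water 'to thirst' and abstain from fluid 'loading".
- On the morning: no compression wear, abdominal binders or support stockings.

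The bar on participation is tied to this list: "If it is decided that individuals are unable to cease the above listed medications for the prescribed time", they cannot take part. The reason given is that "biomarker and autonomic testing outcomes would not be deemed meaningful in the setting of artificial control of heart rate and fluid status".

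Nicotine, smoking, vaping and exertion appear in none of the tiers. Tobacco appears in section 3.16 (Before study testing day, item 3) as part of the "Demographic survey and Medical Health History including alcohol consumption, tobacco use". Medication use is recorded for all three cohorts in the section 2.5 table.

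The heart-rate criterion for POTS, written for Cohort 2 in section 3.6, is a "sustained heart rate elevation of" at least 30 beats/min within 10 minutes. The test is a supine recording followed by 10 minutes of standing (section 3.16, Study Day Testing, item 5).

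**The concern.** Section 2.1 promises prevalence from a standardised autonomic testing protocol. Section 2.6 goes as far as fixing room light and temperature. Caffeine is controlled for 24 hours, but a cigarette or vape just before the stand is not. Nicotine may act on heart rate at the moment of measurement, and the primary outcome depends on a threshold in heart-rate rise, so uncontrolled use could move some people across it.

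The lack of a record matters as much as the lack of a rule. A history item shows who smokes, not who smoked before the test. Without a same-day question, the effect cannot be examined in the analysis.

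Exercise is a separate and lesser matter. Section 2.3 describes Long COVID as including "fatigue, reduced cognition, exercise intolerance, pain and tachycardia in this cohort", so recent strenuous exercise is more likely among healthy controls. It therefore concerns the control comparisons in the secondary aims, not POTS prevalence in Long COVID.

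**Working it through.** **Step 1. The plan's own precision figure.** Section 3.3 gives n = t²·p(1−p)/m² with p = 0.10 and m = 0.05. Putting in 1.96: 3.8416 × 0.09 / 0.0025 = 138.3, rounded up to 139. This reproduces. The yardstick for any bias is therefore ±5 points around 10%.

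**Step 2. The list against the exposures.**

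| Exposure | Preparation rule (section 2.5) | Recorded for the test day? |
|---|---|---|
| Caffeine, alcohol | Stopped at 24 h | Not needed if followed |
| Named drug classes | Stopped at 48 h or 24 h; otherwise barred | Medication use recorded |
| Other prescribed drugs | None | Medication use recorded |
| Tobacco, vaping, other non-prescribed nicotine | None visible | No; tobacco as history only |
| Strenuous exercise | None visible | No |

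The last two rows are the gap.

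**Step 3. Which quantity is affected.** POTS is called on the rise, that is, standing minus supine heart rate. An exposure that raises both equally leaves the rise unchanged. Only the difference between the two effects counts, and the documents give no figure for it.

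**Step 4. Illustrative size.** Inputs from section 3.3: SD 15.5 bpm (the healthy standing group) and 10% prevalence. Assumptions of mine: the rise is normal, the heart-rate threshold alone decides POTS, the exposure shifts the rise by 5 to 10 bpm, and 5% to 20% of Long COVID participants are exposed.

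- Mean rise that puts 10% at or above 30 bpm: 30 − 1.2816 × 15.5 = 10.1 bpm.
- Shift of +5: z = (30 − 15.1)/15.5 = 0.959, so P = 16.9%, a change of 6.9 points per exposed person.
- Shift of +10: z = (30 − 20.1)/15.5 = 0.636, so P = 26.2%, a change of 16.2 points.
- Smallest effect on prevalence: 0.05 × 6.9 = 0.3 points.
- Largest: 0.20 × 16.2 = 3.2 points.

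If the supine rate rose more than the standing rate, the shift would be downward:

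- Shift of −5: z = 1.604, P = 5.4%, a change of −4.6 points.
- Shift of −10: z = 1.927, P = 2.7%, a change of −7.3 points.
- Effect on prevalence: from 0.05 × (−4.6) = −0.2 to 0.20 × (−7.3) = −1.5 points.

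All of these lie within ±5 points.

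**The case against.** **The quoted reason is narrower than the concern.** It explains why people who cannot stop the listed drugs are barred. It is not a general principle about everything that may affect heart rate. This stands: a reader might infer that the protocol contradicts itself, and it does not. The point is an addition in the spirit of the caffeine rule.

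**POTS is judged on the rise, not the standing rate.** This stands, and it is why no direction is claimed.

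**The numbers are assumed.** This stands. The model is also rough: a mean of 10.1 bpm with SD 15.5 puts about 26% of participants below zero, a fall in heart rate on standing. It also ignores the other conditions in section 3.6: a sustained rise, no orthostatic hypotension, no secondary cause, and symptoms for more than three months.

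**A larger effect can be obtained.** A reader might start from the healthy-group mean of 26 bpm in section 3.3. There 39.8% reach 30 bpm unshifted and 65.1% after +10, so 0.20 × 25.3 gives about 5 points, the whole planned precision. The documents do not support that starting point. It is a 30-minute figure from 15 healthy people, while the study test lasts 10 minutes, and it conflicts with the plan's own 10% prevalence.

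**Drugs outside the list.** A reader might infer that other heart-rate-raising drugs are uncontrolled. This is largely covered: anticholinergics and sympathomimetics stop at 48 hours, medication use is recorded, and the control advertisements ask for people not on regular medication. How recorded medication enters the analysis may be left to the statistical analysis plan.

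**The rule may exist elsewhere.** The project schema and the participant information sheet are not visible, so the omission holds for the visible text only.

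**Conclusion.** The point holds as a minor, cheap improvement in measurement. In the visible text, non-prescribed nicotine and strenuous exercise are neither restricted before the test nor recorded on the day. The heart-rate rise that decides POTS can therefore be affected in a way that cannot be examined afterwards.

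Under the stated assumptions, prevalence moves by about 0.3 to 3.2 points if the shift is upward, and by 0.2 to 1.5 points the other way if it is downward. Both ranges are inside the planned 5 points. They rest on a normal rise with SD 15.5, 10% baseline prevalence, a 5 to 10 bpm shift and 5% to 20% exposed; the shift and the exposed share have no source in the documents. The true direction and size are unknown.

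The exercise part applies mainly to the secondary comparisons with controls. A reader might carry it over to the primary prevalence, but controls do not enter that estimate. Sample size is unaffected.

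**What to change.** 1. Add non-prescribed nicotine products (tobacco, vaping and similar) and strenuous exercise to the pre-test restrictions in section 2.5. The investigators should set the windows, in line with the 8-hour and 24-hour windows already there. If the schema or information sheet already covers these items, carry the wording into section 2.5.
2. Ask about both on arrival and record the answer. Where the restriction was not met, rebook or flag the participant.
3. Report POTS prevalence in the Long COVID cohort with and without flagged participants.
4. Stop no prescribed drug on this account, nicotine replacement included. Prescribed drugs outside the list that act on heart rate can be identified from the medication-use item already collected and included in the same sensitivity estimate.

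The cost is two lines in the preparation instructions, a short arrival check and one extra estimate. The downside is a few rebooked visits and mild discomfort for smokers.

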### Study testing day:

The following testing protocol will take approximately 60-90 minutes to complete. A schematic representation of the protocol can be seen (Figure 1: above)

Non-invasive measurements of continuous arterial pressure and heart rate will be obtained using finger photoplethysmography (non-invasive blood pressure testing; NIBP) for 5 minutes before testing (rest) and then during each reflex test. This involves application of a small cuff to either of the 2nd to 5th digits of

one hand. The cuff is inflated to allow measurement of finger arterial blood pressure. This technique is well validated in a variety of clinical and experimental conditions and is similar to our prior protocol. Description of each test can be found in section 3.16

Testing variables	Cohort 1	Cohort 2	Cohort 3
Demographic Survey	X	X	X
Medical health history	X	X	X
Medications use	X	X	X
Physical examination	X	X	X
Health Related QoL			
- SF-36 [36-Item Short Form Survey]	X	X	X
- EQ-5D [5 level EQ score]	X	X	X
- COMPASS-31 [composite autonomic symptom scale]	X	X	X
- FSS [fatigue severity score]	X	X	X
- 5 Point hypermobility screen	X	X	X
- OHQ [orthostatic hypotension questionnaire]	X	X	X
Autonomic testing			
- Standing test, deep breathing, Valsava manoeuvre	X	X	X
- Sudomotor function (SUDOSCAN)	X	X	X
- 24-hour Holter monitoring	X	X	X
- Echocardiogram with Passive Leg Raise	X	X	X
Blood tests:			
- Complete Blood Panel and Electrolytes, CRP, ESR,	X	X	X
# TNF- $\alpha$ , IL-6, IL-1 $\beta$ , IL-10, IL-21, INF $\gamma$ , INF $\alpha/\beta$ , CD30,	X	X	X
# $\alpha$ 1 adrenergic, Beta-1 adrenergic, M1 and M4 muscarinic	X	X	X
cholinergic receptor Ab;			
# Aldosterone, Potassium, Renin activity, copeptin level;	X	X	X
# Plasma Histamine, heparin, chromogranin A	X	X	X
24 hr Urinary volume and osmolarity	X	X	X
Cognitive and psychological testing			
- CANTAB (Cambridge neuropsychological test automated battery)	X	X	X
- HADS (hospital anxiety and depression scale)	X	X	X

## 2.6 Location(s) of the research:

Include details of all sites where the project will be undertaken and locations of participants.

Participant assessments will be undertaken by the Centre for Heart Rhythm Disorders (CHRD) at two sites. The first site is in Norwood, South Australia and the other Cardiovascular Services in Kew East, Melbourne, Victoria. Additionally, controls can undergo their autonomic testing in the clinical rooms at the UoA/SAHMRI, North Tce, Adelaide. This facility provides a clinical setting that is appropriate to the research and allows for added convenience for students who wish to volunteer for the research. No patients will be recruited from public health organisations and no data collection will take place at public health spaces. Due to the scarcity of specialists treating dysautonomia in Australia, many patients access care from interstate via telehealth or interstate visits to the Adelaide clinic. Use of private rooms in Melbourne will facilitate higher enrolment and study participation rates. As Victoria, Australia had one of the largest SARS-CoV-2 infection rates in Australia, it is supposed that there will be higher rates of LCS in this state. All study investigators have appropriate Australian professional registration and indemnity which will cover patient/clinician interaction in both states.

All studies will be undertaken in a quiet, dimly lit room with a comfortable ambient temperature between 21-24 degrees Celsius.

**2.7 If research is to be conducted with or about participants living outside Australia outline any local legislation, regulations, permissions or customs that need to be addressed before the research can commence. Outline the steps taken to ensure that this has been adequately considered and addressed.**

See *National Statement Chapter 4.8*. Attach authorising correspondence and/or approval documentation to the application. If you are travelling to a region classified as level 3 or 4 according to the [Department of Foreign Affairs and Trade](#), travel approval may be required. See The University of Adelaide's [travel safety information in the HSW Policy and Handbook](#).

n/a

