### **3.7 Where will participants be recruited or sourced from?**

Any use of snowball sampling for recruitment should only be in the passive form. That is participants may be asked to discuss the research with friends/contacts who they think may be interested in volunteering to be participants. Those new participants should then contact the research team to volunteer.

Participants will be recruited through social media forums that pertain to support of those with LCS. Administrators of social media platforms for LCS will be approached by senior investigators for permission to post information about the study with contact details for researchers. We recognised the selection bias associated with this method of recruitment, however given the extraordinary nature of the current pandemic and the lack of understanding of LCS and its associated diagnosis and aetiology, it would seem that this bias is justified by the urgent requirement for preliminary understanding of the condition. As this study looks to explore immune, inflammatory and cardiovascular changes rather than efficacy of interventions, the use of convenience sample is more tolerable.

In addition, consecutive patients with POTS who attend [name] practice and The University of Adelaide, Centre for Heart Rhythm Disorders will be recruited. Potential participants may be approached by a member of the clinic/study staff via email introducing the study and providing the plain language patient information sheet explaining the purpose of the study. Healthy controls will be recruited through flyers and posters placed within The University of Adelaide health and education campuses. In addition, healthy controls referred to CHRDC/CVC for investigation of heart arrhythmia (but found to have none) will be recruited via the above mentioned flyers. Advertisements will be placed on the SAHMRI and University of Adelaide facebook sites as per attachment 5.

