#### POTS participants

- Email detailing study outline will be sent to potentially eligible participants. PICF will be attached to the email and patients will be requested to make contact if they are interested in the study.
- University social media and private practice internet advertisements
- Private practice and university flyers (attachment 6)

LCS participants

- Through social media advertisement (attachment 4)

Healthy matched controls will be recruited from

- Patients referred for cardiac evaluation who are healthy via practice flyers (attachments 6)
- Through flyers located at the Centre for Heart Rhythm Disorders facilities in Norwood, Adelaide and North Terrace Campus, University of Adelaide and SAHMRI (attachment 6) As well as facebook pages monitored and run by these organisations to promote current research.

Recruitment Materials: The following materials will be used to recruit participants.

1. Participant Information Sheet in plain language
2. Patient Consent Form
3. Introductory email to POTS patients who attend our private clinic
4. Introductory email and advertisement for social media administrators of support group for those with Long Covid
5. University of Adelaide, SAHMRI and Private Practice internet advertisements
6. Flyers for University and Private Clinic advertisement

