8. 24 hr Urinary volume, sodium and osmolality: At the end of their testing subjects will be given a container and a measuring pot to undertake a 24hr urine sodium, volume and osmolality study. This urine sample will be returned to a designated pathology collection centre the following day.

Information provided in **Question 3.16** should be incorporated into information provided to participants, either through a participant information sheet or other methods as described in **Question 3.11**. University templates for participant information sheets, consent forms and a drugs to be administered form are available at <https://www.adelaide.edu.au/research-services/oreci/human/applications/>.

**3.17 For research that involves the handling, storage, and/or disposal of human biospecimens, please detail below the protocols that will be followed to ensure *National Statement* requirements are met.**

See *National Statement Chapter 3.2*.

- (a) The burdens of the blood and urine collection on the donor(s) are justified by the potential benefits of this proposed research. POTS and LCS have a significant patient burden in terms of reduced quality of life and high community and health care burden. This study has the potential to elucidate biomarkers that inform understanding of disease aetiology, diagnosis and treatment
- (b) Blood and urine collection will be undertaken via a qualified and registered pathology collection service as well as by clinically trained and qualified researchers. These researchers include medical doctors and registered nurses who are experienced in the practices of safe blood collection and will adhere to best practice guidelines for phlebotomy. All blood tests will be undertaken in an appropriate clinical setting.
- (c) Blood specimens will be deidentified, spun in a centrifuge and frozen and stored in locked bio-secure freezers at the South Australian Health and Medical Research Institute to facilitate analysis.

Routine blood and urine samples will be processed in accordance with current guidelines as detailed by the associated pathology group. Blood and urine samples will be labelled with the participants identifying information and then sent to the lab for processing. Once processed, identifying information will be exchanged for a code before results are returned to researchers to ensure de-identification.

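### Every named control recruitment location is in Adelaide, while Melbourne was added partly for Long COVID; site is likely to be unbalanced between LCS participants and controls

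*Protocol*

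**What the plan says.** **Test sites.** Section 2.6 names two sites for all participants, Norwood (Adelaide) and Kew East (Melbourne). It gives two reasons for Melbourne: "Use of private rooms in Melbourne will facilitate higher enrolment and study participation rates", and the supposition about Victoria that "it is supposed that there will be higher rates of LCS in this state". A third venue is for controls only: "controls can undergo their autonomic testing in the clinical rooms at the UoA/SAHMRI, North Tce, Adelaide".

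**LCS recruitment.** Sections 3.3 and 3.7 recruit 150 people through social media and support groups, with no state specified.

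**POTS recruitment.** Section 3.3 takes 34 patients from a specialty clinic of the Adelaide centre. Section 2.6 says that many of the patients treated for dysautonomia come from interstate.

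**Control recruitment.** Section 3.7: "Healthy controls will be recruited through flyers and posters placed within The University of Adelaide health and education campuses". It adds University and SAHMRI Facebook notices. Section 3.8: "Through flyers located at the Centre for Heart Rhythm Disorders facilities in Norwood, Adelaide and North Terrace Campus, University of Adelaide and SAHMRI". Section 3.9 adds the Cardiovascular Centre, which sections 4.5 and 5.11 place in Norwood. One further route names no city: "healthy controls referred to CHRDC/CVC for investigation of heart arrhythmia (but found to have none) will be recruited". The healthy-volunteer notice in Attachment 5 says that testing may be in Melbourne or Adelaide.

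**Matching.** Section 3.4 matches controls on age and gender.

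**Samples.** Section 3.17(c): "Blood specimens will be deidentified, spun in a centrifuge and frozen and stored in locked bio-secure freezers at the South Australian" (the institute meant is SAHMRI). Section 5.5 places the researchers' own assays there too, and sends some routine blood and urine tests to an outside pathology service.

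**The concern.** Secondary objective 2 in section 2.1 compares neuroendocrine, inflammatory and immune markers between LCS, POTS and matched healthy controls. If the LCS cohort is spread over two states and the controls are nearly all in one, a difference between sites in collection, handling or recording conditions adds to the LCS-control difference and looks like disease. Objective 3 has the same exposure for measurements taken at the visit.

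Matching protects against age and gender imbalance but not this one. The mix of sites among controls is fixed once they have been recruited, and the layout of assay plates once they have been run, so both need to be settled before collection and assay.

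**Working it through.** The plan states no figure on this point, so there is none to reproduce. The check is a comparison of the protocol's sections, followed by an illustration.

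**Step 1. Cohort by site.**

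| | LCS (150) | POTS (34) | Controls (34) |
|---|---|---|---|
| Recruited through | support groups, no state | Adelaide centre's clinic, some interstate patients | named locations all Adelaide; one route with no city |
| May be tested at | Norwood, Kew East | Norwood, Kew East | Norwood, Kew East, UoA/SAHMRI |
| Matched on site | n/a | n/a | no |

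Followed as written, the Melbourne share is likely to be higher among LCS participants than among controls.

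**Step 2. Which comparisons are exposed.**
- LCS v controls: exposed.
- LCS v POTS: possibly exposed, because the POTS clinic is in Adelaide.
- POTS v controls: both draw largely on Adelaide sources, so little exposure.
- LCS with POTS v LCS without POTS: one cohort with one recruitment route, so not exposed to this imbalance.
- Prevalence of POTS in LCS (primary objective): no control comparison, so not exposed.

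**Step 3. Illustrative size.** Let p and q be the Melbourne shares in LCS and controls, and d the site shift in SD units. All three are assumed. In an unadjusted comparison

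bias b = (p − q) × d.

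The standard error is s = √{[1 + p(1 − p)d²]/150 + [1 + q(1 − q)d²]/34}. The chance of a false positive at two-sided 5% is Φ(b/s − 1.96) + Φ(−b/s − 1.96). For example, with p = 0.5, q = 0 and d = 0.5: b = 0.25, s = √(1.0625/150 + 1/34) = 0.191, b/s = 1.31, false-positive rate 26%.

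| Melbourne share, LCS v controls | Shift d (SD) | Bias b (SD) | False-positive rate |
|---|---|---|---|
| 50% v 0% | 0.3 | 0.15 | 12% |
| 50% v 0% | 0.5 | 0.25 | 26% |
| 70% v 0% | 0.3 | 0.21 | 20% |
| 70% v 0% | 0.5 | 0.35 | 45% |
| 50% v 20% | 0.3 | 0.09 | 8% |
| 50% v 20% | 0.5 | 0.15 | 12% |
| 30% v 30% | 0.3 or 0.5 | 0 | 5% |

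**Step 4. What adjustment could recover.** Suppose no control is tested in Melbourne. Three groups remain: Adelaide controls, Adelaide LCS and Melbourne LCS. With an additive site shift, the two LCS groups estimate the shift and the two Adelaide groups estimate the LCS effect. The Melbourne LCS participants then add nothing to the LCS-control estimate. Its standard error, in SD units, is √(1/n + 1/34) with n the LCS participants tested in Adelaide, against √(1/150 + 1/34) = 0.190 if all 150 could be used:
- 50% in Melbourne, n = 75: 0.207, or 9% larger.
- 70% in Melbourne, n = 45: 0.227, or 20% larger.
- 90% in Melbourne, n = 15: 0.310, or 63% larger.

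A term for state would not remove any difference between Norwood and the UoA/SAHMRI rooms, where no LCS participant is tested.

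**The case against.** The strongest case on the other side is that the imbalance is only plausible, and that ordinary adjustment deals with it. Attachment 5 offers controls testing in Melbourne, section 3.3 mentions private medical campuses with no city, and the UoA/SAHMRI rooms are optional. LCS participants seen in both states would let an additive site shift be estimated even with no Melbourne controls, at a small cost in precision unless the Melbourne share is high (Step 4). A site term belongs in an SAP, which is not at hand, so its absence is no finding. Most of this stands. It makes the confounding partial but does not secure a single control at Kew East.

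A reader might also infer several stronger things that the protocol does not support:
- *That LCS participants come mainly from Melbourne.* Section 2.6 supposes higher rates in Victoria and gives no share.
- *That every biomarker comparison is confounded.* Step 2 shows otherwise, and some routine blood and urine tests do not go to SAHMRI at all.
- *That no later analysis could separate site from disease.* This would be so only if there were no overlap, with every LCS participant in Melbourne and every control in Adelaide.
- *That control blood is spun at once while Melbourne blood travels unspun.* The wording in section 3.17 can be read as locating only the freezers at SAHMRI. Local spinning and frozen shipment would fit it, Norwood samples must travel too, and section 2.6 names the SAHMRI rooms only for autonomic testing.
- *That equipment differs by cohort.* No section says so. One centre runs the assessments, with the same tests and the same room conditions.

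**Conclusion.** The point holds in limited form. The named control locations, the controls-only venue, the reason given for the Melbourne site and matching that ignores site together make an LCS-control site imbalance likely. The same may apply to LCS v POTS. What is exposed is the set of research biomarkers stored and assayed at SAHMRI, together with recordings that depend on site.

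The size cannot be derived from the protocol. The bias of 0.15 to 0.25 SD at 50% v 0% rests on assumed shares, an assumed shift of 0.3 to 0.5 SD and an unadjusted comparison. It shrinks as the control mix approaches the LCS mix and is zero when they are equal. Adjustment could remove an additive shift between states, but without Melbourne controls it leaves the Melbourne LCS participants out of the LCS-control estimate. It therefore does not fully replace recruiting controls at both sites. The absence of a draw-to-freeze rule would be mere missing detail if it stood alone; it matters here because samples come from two states.

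**What to change.** 1. In sections 3.7 and 3.8, and in the matching sentence in 3.4, add Kew East to the control flyer and advert locations. Aim for a control site mix similar to that of the LCS cohort, by frequency matching on state alongside age and gender.
2. In sections 3.17 and 5.5, state that samples from all cohorts and both states are distributed across each ELISA and multiplex plate.
3. In the same sections, apply one draw-to-freeze procedure at every site and record the times.

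The cost is that some control visits move to Melbourne, with modest logistics for recruitment and sample transport. No extra participants or tests are needed.
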